7.2.2 Ophthalmic Procedures

Best-Corrected Visual Acuity (BCVA)/Refraction (Distance Measurement)

BCVA measurement should be performed on both eyes using the Electronic ETDRS (E-ETDRS) Visual Acuity Testing Protocol.⁴⁸ These will be performed by a study certified examiner. Traditional ETDRS charts may be used if the E-ETDRS chart is not available. BCVA and refraction will be done via protocol by a study certified examiner.

Best Distance-Corrected Near Visual Acuity (Near Measurement)

In order to evaluate the potential of ALA to improve presbyopia, a distance-corrected near visual acuity will be measured with a near vision ETDRS style chart. Using the distance correction (based on refraction), the near visual acuity will be measured for each eye with the near vision chart held at 16 inches (40 cm). This should be done regardless of the eye being phakic or pseudophakic.

Ophthalmoscopic Examination

Intraocular pressures (IOP) will be measured at each study visit. Pupils will be dilated with two sets each of 2.5% Neo-Synephrine and 1% Mydracyl, or equivalent. A complete anterior and posterior segment slit lamp exam will be performed by the study certified ophthalmologist including a lens assessment. This will be done with both a slit lamp and dilated ophthalmoscopy.

7.2.3 Photography

Keratometry

Automated or manual keratometry measurements will be made at the baseline screening visit. The corneal radius of curvature for each eye of each subject will be entered into the Heidelberg Spectralis machine. From the keratometry measurements, the average keratometry reading (K) for each eye is calculated $[(K1 + K2)/2]$. Then, the corneal radius of curvature (mm) can be calculated using the formula

CONFIDENTIAL

and the average K measurement: $r = 337.5/K$. Keratometry measurements will be re-measured and updated within the Spectralis if a subject has had any ophthalmic surgery or history of corneal suture removal since the last study visit.

Fundus Photography

A photographic field between 30 and 40 degrees is required. Stereo color photographs of standard fields 1, 2 and modified 3 will be obtained. Photographs from baseline, months 6, 12, and 18 will be read by the Scheie Image Reading Center for an independent assessment. Fundus photos should be acquired before fundus autofluorescence images are acquired.

Spectral Domain Optical Coherence Tomography (OCT)

All OCT images from enrollment (baseline) and months 6, 12, and 18 months will be read by the Scheie Image Reading Center for additional outcomes. These images will be acquired with the Heidelberg Spectralis (Carlsbad, CA).

Fundus Autofluorescence (FAF)

The areas of geographic atrophy will be evaluated from FAF images taken with the Heidelberg Spectralis (Carlsbad, CA) using the Blue Peak Blue Laser Autofluorescence mode. The FAF images should be taken after the color fundus photos and OCT imaging.

All FAF images from enrollment (baseline) and months 6, 12, and 18 will be read by the Scheie Image Reading Center.

Geographic Atrophy

Geographic atrophy (GA) will be assessed from the color fundus photographs and FAF images. On color photographs, GA is observed as one or more sharply defined, more or less circular patches of absence of the RPE, typically with exposure of underlying large choroidal blood vessels. At a minimum, at least two of the aforementioned characteristics (sharp edges, more or less circular shape and visibility of underlying choroidal vessels) with a minimum size of ≥ 175 microns in longest linear dimension are required for a lesion to be categorized as GA.⁴⁹ While a minimum size of ≥ 175 microns in longest linear dimension is required for a lesion to be categorized as GA for grading once an eye is in the study, the GA size requirements for study eye inclusion stated in section 4.2.1 (Inclusion Criteria) still stand.

Once geographic atrophy has been identified on the color photographs and FAF by the grader, the grader will use the Region Finder semi-automated software of the Heidelberg Spectralis to measure the areas of geographic atrophy at the macula of the study eye. While the color photographs are used to categorize a lesion as GA, the primary measure of GA area will be taken from the FAF images. The color photos can also be used to assist in the interpretation of the FAF images. GA appears as well defined hypoautofluorescent patches in FAF images. All areas of GA at the macula of the study eye will be measured.

CONFIDENTIAL

7.3 Follow Up Phase of the Study

7.3.1 End of Study Visit

Two weeks following the 18 months visit, the subject will be contacted to determine if there have been any adverse events following the completion of the study and to ensure that the subject has a follow-up eye examination (outside of the study) with an ophthalmologist.

7.4 Unscheduled Visits

Unscheduled visits will be handled as typical standard of care visits by the treating ophthalmologist. Any exams and tests at unscheduled visits will be billed to the subject's insurance per the usual practices of that ophthalmologist. At the next scheduled study visit, any adverse events related to the need for the unscheduled visits will be recorded. If there is a significant change in exam or a new diagnosis noted at the time of the unscheduled visit (i.e. new choroidal neovascularization, retinal vein or artery occlusion, vitreous hemorrhage, etc.), the Sponsor will be notified

7.5 Subject Withdrawal

Subjects may withdraw from the study at any time without impact to their care. They may also be discontinued from the study at the discretion of the Investigator for lack of adherence to intervention or study procedures or visit schedules, AEs, or due to other concerns. The Investigator or the Sponsor may withdraw subjects who violate the study plan, or to protect the subject for reasons of safety or for administrative reasons. It will be documented whether or not each subject completes the clinical study. Subjects who wish to withdraw early will be asked to have one final visit to collect investigational product and to follow up regarding adverse events before formal withdrawal of consent.

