5.8 Subject Compliance Monitoring

Each Investigator must make visits as pleasant as possible by minimizing wait time and providing comfortable waiting and examination facilities. The Investigator for each Clinical Center will continually educate the subjects as to the nature of the study, the need for the subject’s continued participation, and answer questions concerning geographic atrophy and the use of ALA.

In Phase 2, subjects will be contacted to remind them of a follow up visit within the week of the appointment. The contact can be by telephone or email and a subject response is necessary. To ensure subject compliance for scheduled visits, early morning, evening, or weekend hours may be provided. Every effort must be made by the Investigator to remain in contact with subjects, even if they do not want to return to be examined or follow the protocol. After subjects enrolled in Phase 2 are randomized, they will be contacted at week 2 and months 1, 3, 9, and 15 months to ensure study drug compliance and to inquire about any difficulties with the study drug.

If a subject cannot tolerate the study medication (ALA or placebo) because of gastric reflux or symptoms thought to be from gastric reflux, they will be encouraged to prevent their symptoms by taking an over-the-counter gastrointestinal medication for reflux such as ranitidine or omeprazole. The investigator will make the determination that the symptoms are consistent with reflux and make the recommendation for gastrointestinal prophylaxis on a case-by-case basis. The investigator may choose to involve an internist in making this decision. Any use of gastrointestinal prophylaxis medications will be recorded. If ranitidine is desired to treat such symptoms at no cost to the subject because of reflux presumed to be related to the study medication, then a prescription may be sent (fax/email) to the UPenn IDS and the ranitidine will be mailed to the subject. The study’s Clinical and Scientific Expert must be notified and approve of this action within one week and prior to sending the ranitidine prescription to the Penn IDS.

If a subject cannot tolerate the study medication (ALA or placebo) for the reasons detailed below, then the subject will be asked if he/she is willing to take one capsule twice daily instead of two capsules once daily:

- there are uncomfortable gastrointestinal symptoms that do not resolve with medication for reflux,

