- there are gastrointestinal symptoms and the subject does not want to take any prophylactic gastrointestinal medication, or

CONFIDENTIAL

- there are other symptoms causing intolerance of the study dose

If the subject cannot tolerate or does not want to take one capsule twice daily, then the subject will be asked if he/she is willing to take one capsule once daily. If the subject cannot tolerate one capsule once daily or does not want to take one capsule once daily, then the subject will be asked to at least remain in the study. All changes to the schedule of study medication dosing will be documented.

The study subjects will be asked to provide urine samples at the 12 months study visit. The urine will be tested for a metabolite of ALA to determine the subject's compliance. The samples will be tested in the Metabolomic Core Laboratory directed by [name] at the Children's Hospital of Philadelphia (CHOP). Please follow the instructions below for shipping of urine samples from each site to the Scheie Eye Institute lab for storage before analysis.

Instructions for shipping and handling of urine analysis samples:

Samples must be frozen (in a -20 °C freezer, shipping labels will be provided, samples must be shipped frozen on dry ice via overnight carrier to:

[name] Laboratory
University of Pennsylvania
[name]
[name]
[name]

Contact Information:

Office: [contact]

Email: [contact]

Urine samples will be stored in a freezer in the [name] Laboratory at -20 °C or less. The temperature of this freezer should not drop below -20 °C.

The collected urine samples will be transferred on dry ice to:

The Children's Hospital of Philadelphia (CHOP) Abramson Research Center (ARC) 5TH Floor,
[name]
[name]
[name]

Contact information:

[name],

Email: [contact]

[contact]

or

[name],

Email: [contact]

[contact]

[contact]

For questions please contact:

[name]

Metabolomic Core Director

Email: [contact]

The samples will be transferred from the [name] lab to the [name] lab in a total 2-3 batches with the first batch sent after 35% or more of samples have been collected.

CONFIDENTIAL

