7.2 Study Intervention Phase

7.2.1 6 Month, 12 Month, and 18 Month Visits

Fundus photographs, OCT and FAF images will all be collected at enrollment (baseline), 6, 12, and 18 month visits only. Both eyes will be imaged. These will be collected by ophthalmic photographers certified for clinical trial imaging. The Scheie Eye Institute Reading Center will provide detailed grading of FAFs, color fundus photographs, and OCTs for determination of study outcomes. Color fundus photographs, FAF and OCT images will be submitted to the Scheie Image Reading Center at enrollment (baseline), 6, 12, and 18 months. At each of these visits, the subject will be given the option of completing the Ocular Surface Disease Index (OSDI).⁴⁷

Study visits must fit the recommended time frame as much as possible. All follow-up study visits must at least be within 3 months (+/- 3 months) of the recommended date of the study visit.

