7.6 Early Termination Visits

If a subject terminates the study early, a follow-up visit will be scheduled to assess subject safety and collect unused drug. The reason for early termination will be recorded on the case report form. AEs and SAEs will be recorded. The Investigator will ensure that the subject has a follow-up standard-of-care visit scheduled with an ophthalmologist for their continued eye care.

8 Statistical Plan

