8.3 Sample Size and Power Determination

Phase 1: It is expected that a sample size of 15 subjects will adequately determine if there is a significant intolerance of the tested doses of ALA in the elderly population.

Phase 2: In addition to assessing the safety profile of ALA and the feasibility of study procedures, one of the major goals of the proposed study is to determine if additional, larger scale assessments of efficacy are warranted. For pilot studies, it is appropriate to use a confidence interval approach to evaluate outcomes and pre-specify a clinically important threshold to determine if further investigation is justified.⁵⁰⁻⁵¹ If we decide to halt investigation if the observed growth rate in the actively treated group is greater than in the placebo group, then it is reasonable to use a one-sided confidence interval. With 50 total subjects, we can be 90% confident (one-sided) that the “effect size” of ALA in reducing the GA growth rate is 0.4 or less. This number assumes that 15% of subjects dropout. An example of an effect size of 0.4 would be a growth rate of 0.40 mm in the placebo group and a growth rate of 0.32 (20% reduction) in the ALA group when the standard deviation of the annual growth rate is 0.20 mm.⁵² Interventions with less efficacy than this may not be worth pursuing.

Based on current data, it is possible that approximately 25% of subjects randomized to the ALA arm may not tolerate 1200 mg of ALA. Instead of 1200 mg once daily of ALA, some of these patients may elect to take 600 mg twice daily or 600 mg once daily. An intention to treat analysis will be performed on all subjects randomized to 1200 mg ALA in comparison to the placebo group. Subgroup analyses will be performed on those subjects remaining at 1200 mg and subjects at a lower dose of ALA. After 25 subjects have enrolled in the study, we will perform interim analyses of the numbers of subjects in these subgroups without evaluating any outcomes data. Depending on the status of enrollment, drop-out rates, and the size of the subgroup consistently taking 1200 mg subgroup, the study sample size may be increased at this time so that the 1200 mg subgroup has a number equal to or nearly equal to 22 subjects available for analyses.

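### Section 7.5 lets sites or the Sponsor remove randomised Phase 2 subjects from the study, not only from study drug, which sits badly with 5.8 and with intention to treat

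*Combined protocol and SAP*

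**What the plan says.** **Removal.** Section 7.5 belongs to the Phase 2 procedures. It says of subjects: "They may also be discontinued from the study at the discretion of the Investigator for lack of adherence to intervention". The same sentence adds non-adherence to procedures or visits, adverse events and other concerns. The next one reads "The Investigator or the Sponsor may withdraw subjects who violate the study plan", and also allows withdrawal for safety or administrative reasons. What ends is participation in the study; stopping study drug is not treated as a separate event.

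**Retention.** Section 5.8 tells investigators to try to "remain in contact with subjects, even if they do not want to return to be examined or follow the protocol". It sets out steps for subjects who cannot tolerate the capsules. For those who cannot or will not take even one capsule a day, "then the subject will be asked to at least remain in the study".

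**Imaging.** Section 7.2.1: "Fundus photographs, OCT and FAF images will all be collected at enrollment (baseline), 6, 12, and 18 month visits only". Section 7.6: "If a subject terminates the study early, a follow-up visit will be scheduled to assess subject safety and collect unused drug"; it also records adverse events and the reason for termination. Section 7.5.1, on withdrawal of consent, covers return of drug and survival status.

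**Analysis.** Section 8.3: "An intention to treat analysis will be performed on all subjects randomized to 1200 mg ALA in comparison to the placebo group". It also expects that "approximately 25% of subjects randomized to the ALA arm may not tolerate 1200 mg of ALA". Section 8.4 compares rates of change with a mixed effects model and plans multiple imputation as a sensitivity analysis.

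**The concern.** Intention to treat needs outcomes from subjects who stop or change treatment as well as from those who continue. A subject who stops taking capsules is asked by 5.8 to stay and may be removed under 7.5. Two sites could handle identical subjects differently, and both would be within the protocol. If the subject is removed, nothing in the plan calls for further FAF images, so the primary outcome is lost from someone who might have kept attending.

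The loss matters more if it differs between arms. Intolerance of ALA is a plausible reason why it might. The run-in does not screen for that, because its capsules are placebo (7.1).

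**Working it through.** **1. Does any section provide FAF after removal?**
- 7.2.1 ties imaging to four scheduled visits.
- 7.5 gives subjects who wish to withdraw a final visit for drug return and adverse events.
- 7.5.1 adds survival status.
- 7.6 lists safety, adverse events and drug return.

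None mentions imaging. That removal ends FAF collection is therefore an inference from silence, but no section points the other way.

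**2. Which ground in 7.5 could act differently by arm?** Non-adherence and plan violation could arise in either arm. Intolerance is the only arm-specific reason that the documents supply, and it would act mainly through adverse events or other concerns. A remedy limited to non-adherence and plan violations would miss that route.

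**3. What does the planned analysis recover?** The mixed model keeps images taken before removal. A subject removed before month 6 has only a baseline image and says almost nothing about growth. For the rest, the mixed model and standard multiple imputation remove bias only if the lost values are missing at random given what was observed.

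**4. Can the bias be sized?** In a simple comparison of retained subjects, an arm's mean shifts by f × g. Here f is the fraction of the arm removed with no follow-up image, and g is the difference in mean growth, in SD, between removed and retained subjects. The treatment comparison shifts by the difference between the arms' shifts. It is zero if g is zero, or if f and g are the same in both arms, and smaller where earlier images exist. The documents give neither f nor g, so no figure is offered.

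**5. Precision.** Inputs from 3.1 and 8.3: 50 subjects, 1:1 allocation, one-sided 90% confidence, 15% dropout, effect size 0.4 from (0.40 − 0.32)/0.20, SD 0.20 mm per year.

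Half-width in SD units = z × √(1/n₁ + 1/n₂), with z = 1.2816.

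The plan's figure first: n = 25 × 0.85 = 21.25 per arm, and 1.2816 × √(2/21.25) = 0.393. With a t quantile it is 0.400. The stated 0.4 is reproduced.

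| Total loss | Subjects left | Half-width (z) |
|---|---|---|
| 0% | 50 | 0.363 |
| 15% (plan) | 42.5 | 0.393 |
| 20% | 40 | 0.405 |
| 25% | 37.5 | 0.419 |
| 30% | 35 | 0.433 |

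Loss rates above 15% are assumptions. Going from 15% to 20% means 10 − 7.5 = 2.5 more subjects lost and adds 0.405 − 0.393 = 0.012 SD, or 0.012 × 0.20 = 0.0024 mm per year. The calculation takes one independent unit per subject and counts a lost subject as contributing nothing, so it overstates the cost where earlier images exist.

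**The case against.** The case for leaving the text alone has real weight.

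- **Section 7.5 is permissive.** It says what may be done, and a site can follow both it and 5.8. Near-identical sentences serve the open-label Phase 1 in 6.5, which suggests general template wording, whereas 5.8 has specific Phase 2 steps that favour retention. A reader might infer a flat contradiction; the documents do not support that. They leave open which course a site takes.
- **Intolerant subjects are already provided for.** Following the steps in 5.8 is not a plan violation, and 8.3 plans a subgroup of subjects at a lower dose, so it expects them to stay. A reader might take the 25% intolerance figure (6.25 of 25 ALA subjects) as a removal rate. It is not one.
- **Safeguards exist.** Subjects and the research team are blinded (5.6), the run-in screens out general non-adherers, and the mixed model and multiple imputation use the available images. This limits the harm, although blinding does not stop symptom-driven removals from differing by arm.
- **Precision can be protected.** Section 8.3 allows the sample size to be increased after 25 subjects enrol, with drop-out rates among the considerations. That can restore numbers but does not correct selective loss. A reader might infer that a couple of extra losses break the design because the half-width passes 0.400. The plan states 0.4 to one decimal, 0.405 still rounds to that, and nothing says investigator removals fall outside the 15%.
- **The imaging gap rests on silence.** The word limiting imaging to the scheduled visits does not bar a subject who is off drug from attending them. That is true, and it is why a clarification is enough.

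**Conclusion.** The point holds as a tension to be reconciled. Section 7.5 permits removal from the study on grounds that need only concern study drug; 5.8 asks for many of the same subjects to be kept; and 8.3 depends on their outcomes. Removals under 7.5 would cause avoidable loss of the primary FAF outcome, on the inference that nothing is imaged afterwards.

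The loss could differ by arm if intolerance leads to removal. Its direction and size cannot be derived from the documents, and it may be nil. The effect on precision is modest: 0.393 at the planned dropout against 0.405 at an assumed 20% total loss.

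A reader might go further and say that intention to treat is void. It is not: removal is discretionary, images already taken stay in the analysis, and only removed subjects who would still have attended are lost unnecessarily. The comparison is weakened. The wording is worth correcting because the remedy is cheap and the trial has only 50 randomised subjects.

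**What to change.** Reconcile 7.5 with 5.8 and 8.3 by treating stopping study drug and leaving the study as separate events. State in 7.5 that stopping or reducing study drug for any reason (non-adherence, adverse events or other concerns), or a plan violation, does not by itself end outcome follow-up. These subjects continue the imaging already scheduled at 6, 12 and 18 months unless they withdraw consent, are lost to follow-up, or have a safety reason to stop assessments. The wording must cover every reason for stopping drug, because intolerance would mostly enter through adverse events and other concerns. Rules for stopping or changing capsules are untouched.

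The cost is minor protocol wording and visits already planned, with no new procedure. The gain is limited to subjects who still attend; those who stop coming cannot be imaged whatever the text says.

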7.5.1 Data Collection and Follow-up for Withdrawn Subjects

Subjects who wish to withdraw consent to participate in the study will be asked to have one final visit to collect the investigational product. During this visit they will be asked for permission to have the study team look into their survival status via publically available means.

7.6 Early Termination Visits

If a subject terminates the study early, a follow-up visit will be scheduled to assess subject safety and collect unused drug. The reason for early termination will be recorded on the case report form. AEs and SAEs will be recorded. The Investigator will ensure that the subject has a follow-up standard-of-care visit scheduled with an ophthalmologist for their continued eye care.

8 Statistical Plan

